### 5.8.2.1 Primary Analysis of Primary Efficacy Variables(s)

The LMM for the BPI-SF interference score will have treatment as a fixed effect and the study participant ID will be included as a random effect.

The following additional fixed effects will be included:

- Treatment Period (1 or 2)
- assessment number within the period (1st, 2nd, or 3rd assessment categorical) number corresponding to Visit 7, 11, and 15 for Treatment Period 1, or Visit 19, 23, or 27 for Treatment Period 2)

- an interaction of treatment by assessment number
- an interaction of assessment number-by-Treatment Period

The following covariates will also be included:

- BPI-SF interference scores at Baseline (taken at Visit 3, prior to dosing)

The model can also be written as follows:

$$Y_{ij} = Y_{i,bl} + \text{Period}_{ij} + \text{Assessment}_{ij} + \text{TRT} + \text{Assessment}_{ij} \times \text{TRT}_{ij} + \text{Period}_{ij} \times \text{Assessment}_{ij} + (1|s_i)$$

Where  $Y$  indicates the measurement of interest (BPI-SF interference score in this case),  $i$  the  $i$ -th participant,  $j$  the  $j$ -th observation for each participant,  $\times$  indicate an interaction, and  $(1|s_i)$  indicate the random intercept effect for participant  $i$ .  $Y_{i,bl}$  indicates the baseline value for participant  $i$ . Note that this model is specified as-is for conceptual clarity, but is over-parameterized, which may need to be taken into account during model fitting.

The model will utilize an unstructured covariance pattern for the repeated measures. If the model does not converge using the unstructured pattern, then an autoregressive covariance structure will be used. The Kenward-Roger approximation will be used to estimate the denominator degrees of freedom.

The LS Means estimate for each of the treatments with 95% CI should be reported. LS Means should be estimated assuming assessment effects of assessment 3 and using the period effect for period 2. In addition, the LS Means estimate of the differences between rozanolixizumab 12 weeks and 24 weeks, respectively, and placebo should be reported, using the same period and assessment effects as before.

- Rozanolixizumab 12 weeks – Placebo
- Rozanolixizumab 24 weeks – Placebo
- Rozanolixizumab 12 weeks- Rozanolixizumab 24 weeks

P-values for the baseline, treatment period, assessment number, treatment by assessment number, and treatment period by assessment number interaction terms will be reported.

All study participants in the FAS with Baseline BPI-SF score and one or more post-Baseline assessments will be included in the model.

Inter current event (ICE): Permanent discontinuation of treatment will be handled using a hypothetical strategy assuming that the study participants did not experience the events, with data following discontinuation excluded from analysis.

In addition, summary statistics of all results at assessment number 3 (in Treatment Periods 1 and 2) for all participants included in the model will be reported in the primary efficacy table by treatment group.

### 5.8.2.2 Secondary Analysis of Primary Efficacy Variable(s)

As secondary analysis strategy, each period will be analyzed separately using a mixed effect model, with study participant as random effect and treatment, assessment number, treatment by

assessment number interaction, and Baseline as fixed effects. For Treatment Period 1, there will be 2 treatment groups: placebo and rozanolixizumab. For Treatment Period 2, there will be 3 as defined for the primary analysis.

The LS Means estimate for each of the treatments with 95% CI should be reported, as well as the LS Means estimate of the differences between relevant treatment groups. See below treatment differences to be estimated at by period analysis.

Treatment Period 1;

- Rozanolixizumab 12 weeks – Placebo 12 weeks\_Seq2 (between Seq1 and Seq2)
- Rozanolixizumab 12 weeks – Placebo 12 weeks\_Seq3 (between Seq1 and Seq3)
- Rozanolixizumab 12 weeks – Placebo 12 weeks (between Seq1 and pooled placebo from Seq2 and Seq3)

Treatment Period 2;

- Rozanolixizumab 24 weeks – Placebo 24 weeks (between Seq1 and Seq3)
- Rozanolixizumab 12 weeks - Rozanolixizumab 24 weeks (between Seq2 and Seq1)
- Rozanolixizumab 12 weeks – Placebo (between Seq2 and Seq3)

P-values for the baseline, assessment number, and treatment by assessment number interaction should also be reported.

In addition, summary statistics of all results at assessment number 3 (in Treatment Period 1 and 2, as appropriate) for all participants included in the model will be reported in the secondary analysis summary tables.

### **5.8.3 Supportive and Sensitivity Analyses of the Primary Efficacy Variable**

As a sensitivity analysis to evaluate the assumption of treatment effect being independent from site, site (center) will be included in the primary analysis model as an additional covariate. Other covariates may be included if considered appropriate.

The primary analysis of the primary efficacy endpoint will be repeated as an additional sensitivity analysis, using the same ICE strategy as described in [Section 5.8.1](#). This analysis will be based on the study population which includes all participants in the FAS who have received at least 80% of the doses of randomized study medication (up to the point of withdrawal or completion), per treatment period. Note that for participants randomized to rozanolixizumab, mock infusions which are given as a result of temporarily discontinuing IMP will be classified as a ‘missed’ dose. In addition, summary statistics of all results at assessment number 3 (in Treatment Periods 1 and 2) for all participants included in the model will be reported in the sensitivity analysis tables.

### **5.8.4 Derivations of Secondary and Exploratory Efficacy Variables**

Analyses of the following secondary efficacy endpoints will be conducted using an LMM in the same way as for the primary estimand analysis, using the same ICE strategies:

- FIQR total score after 10 weeks of treatment

---

- FIQR individual domain score (activities, overall impact and symptoms) after 10 weeks of treatment
- Mean 7-day pain score (NRS) after 12 weeks of treatment (collected during the 12th week).
- Mean 7-day fatigue score (Fatigue NRS) after 12 weeks of treatment (collected during the 12th week).

For these endpoints, the time points to be used for analysis and baseline are as described in [Table 5-8](#); the value taken at Week 11 (Visit 13) will be used as the measure of treatment effect for FIQR after 10 weeks of treatment for Treatment Period 1, while the FIQR assessed at Week 23 (Visit 25) will be used as the measure of treatment effect after 10 weeks of treatment for Treatment Period 2. Any FIQR assessments which are not completed within the protocol defined window of the scheduled visit will not be included within the efficacy analysis.

Note that for NRS, the participant will be asked at Visit 14 and Visit 26 to complete the pain and fatigue NRS assessment for that day and every day for the following 6 days, and the average of these 7 measurements will be taken as the endpoint. A minimum of 3 valid records among 7-day assessments is required to use participant's average score. The scores measured at Visits 7, 11, and the average of Visit 14 and the following 6 days for Treatment Period 1, and Visit 19, 23, and the average of Visit 26 and the following 6 days for Treatment Period 2 will be used within the LMM.

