ⁱ Daily 24-hr pain and fatigue assessments to be collected every day for a week. Within the Screening Period, the daily average pain over the previous 24 hours will be captured using the Pain NRS through a diary over a 10-day period. Study participants require a minimum of 7 out of the 10 daily Pain NRS assessments over this 10-day period to be eligible for randomization.

^j The 24-hr pain and fatigue assessments to be collected for that day only.

^k To be performed before IMP dosing.

^l Study participants to provide their usual range doses of analgesics PRN.

^m On dosing days, PK, ADA, and IgG will be taken pre-dose.

ⁿ Total IgG only.

^o 80mL at Visit 3.

^p Samples for serum complement (C3, C4) and plasma complement (C3a, C5a) are collected predose at Visit 3 (Day 1) for all study participants. In study participants who experience an infusion reaction or hypersensitivity reaction at site, samples should also be taken 2 hours and 4 hours after the onset of the event, or otherwise as soon as possible but prior to the next dose.

^q 10mL at Visit 1 and Visit 3. In study participants who experience severe and/or serious headaches or suspected aseptic meningitis, exploratory biomarker samples should also be taken 4 hours after the onset of the event, or otherwise as soon as possible within 72 hours after the onset of the event.

Table 1-2: Schedule of Activities (Period 2 through End of Study)

Procedure	12-week Treatment Period: 2												Run-out	Run-out	EOT/EW	SFU/EOS
Visit number	15	16	17	18	19	20	21	22	23	24	25	26	27	28	-	-
Visit window	±2d	±2d	±2d	±2d	±2d	±2d	±2d	±2d	±2d	±2d	±2d	±2d	±2d	±2d	±7d	±7d
Week	13	14	15	16	17	18	19	20	21	22	23	24	25	26	28	32
Day	85	92	99	106	113	120	127	134	141	148	155	162	169	176	190	218
C-SSRS ^a	X												X		X	X
Urine pregnancy test	X				X				X				X		X	X
Laboratory assessments (full hematology, chemistry, urinalysis)	X				X				X				X		X	
Vital signs (blood pressure, pulse and temperature at every visit) ^b	X	X	X	X	X	X	X	X	X	X	X	X	X	X	X	X
Full physical examination ^c															X	X
Brief physical examination ^c	X												X			
Full neurological examination ^d															X	X
Pain NRS	X ^e	X ^e	X ^e	X ^e	X ^e	X ^e	X ^e	X ^e	X ^e	X ^e	X ^e	X ^f	X ^f	X ^e	X ^e	
BPI-SF	X				X				X				X		X	X
FIQR			X				X				X			X	X	X
Fatigue NRS	X ^e	X ^e	X ^e	X ^e	X ^e	X ^e	X ^e	X ^e	X ^e	X ^e	X ^f	X ^f	X ^f	X ^e	X ^e	
Pressure pain threshold ^g	X												X		X	X

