## 1.2 Study Design

This is a Phase 2A, multi-center, randomized, double-blind, placebo-controlled, proof-of-concept study to evaluate the efficacy, safety, PK, and PD of rozanolixizumab for the treatment of severe FMS. Study participants who have a confirmed diagnosis of FMS and have been diagnosed for at least 6 months, with symptoms for at least 2 years before enrollment will be considered for the study.

Study participants enrolled under Protocol Amendments 1 and 2, must meet the following criteria during the Screening Period:

- BPI-SF interference score  $\geq 6$
- FIQR score  $\geq 64$
- Fatigue NRS score  $\geq 5$
- Completed a pain management program of at least 36 hours duration, completion must have been  $>6$  months from study entry date
- Mean daily average 24h pain intensity  $\geq 5$  and  $<10$  assessed by Pain NRS for at least 7 of the last 10 consecutive days of the Screening Period.
- Pain NRS scores  $\geq 4$  at all completed assessments in the last 10 consecutive days of the Screening Period.

Study participants enrolled under Protocol Amendment 3 must meet the following criteria during the Screening Period:

- BPI-SF interference score  $\geq 6$
- Mean daily average 24 hours pain intensity  $\geq 6$  and  $<10$  assessed by Pain NRS. This will be assessed over a 10-day period within the Screening Period. Study participants require a minimum of 7 out of 10 assessments over the 10-day period.
- Pain NRS scores  $\geq 4$  at all completed assessments within the 10-day period.

[figure not shown]
In total and allowing for a dropout rate of 25%, approximately 60 study participants are planned to be enrolled and randomized in the study at up to 8 centers from the UK, with a target of 48 study participants completing the study.

The study will consist of a Screening Period of up to 28 days, a 2-week, single-blind Run-In Period, 2 subsequent 12-week, double-blind Treatment Periods, followed by a 2-week, single-blind Run-Out Period and a 5-week SFU Period.

Study participants will be randomized in a 1:1:1 ratio to 1 of 3 sequences. The study participants in each sequence will receive the following treatment regimen during the double-blind Treatment Periods (see [Figure 1-1](#)):

- Sequence 1: Rozanolixizumab 560 mg sc QW for 24 weeks (12 + 12 weeks Treatment Period) (N=20, Group 1)
- Sequence 2: Placebo sc QW for 12 weeks, followed by rozanolixizumab 560 mg sc QW for 12 weeks (N=20, Group 2)

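### Pain and Fatigue NRS: the autoregressive fallback should allow a different variance at assessment 3, because that assessment is a 7-day mean and the other two are single-day scores

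*SAP*

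**What the plan says.** SAP 5.8.4 defines the NRS data for the model. In Treatment Period 1 they are "The scores measured at Visits 7, 11, and the average of Visit 14 and the following 6 days for Treatment Period 1"; in Treatment Period 2 they are Visits 19, 23 and the seven-day average starting at Visit 26. On completeness it adds: "A minimum of 3 valid records among 7-day assessments is required to use participant's average score". The footnotes to the schedule of activities (Protocol 1.3) that apply to Visits 7, 11, 19 and 23 read: "The 24-hr pain and fatigue assessments to be collected for that day only".

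The model is carried over from the primary endpoint: "Analyses of the following secondary efficacy endpoints will be conducted using an LMM in the same way as for the primary estimand analysis". SAP 5.8.2.1 gives the primary model a participant random intercept and says "The model will utilize an unstructured covariance pattern for the repeated measures". It then provides for failure: "If the model does not converge using the unstructured pattern, then an autoregressive covariance structure will be used". Neither section says whether the autoregressive form has equal or unequal variances. The result is read at one assessment: "LS Means should be estimated assuming assessment effects of assessment 3 and using the period effect for period 2".

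**The concern.** A mean of three to seven daily scores varies less than one daily score unless there is no day-to-day noise. The third NRS assessment in each period is therefore more precise than the first two. BPI-SF and FIQR do not share this feature, since each is the same measurement at every visit. A fallback that suits the primary endpoint has been carried over to endpoints with a different variance pattern.

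Standard AR(1), with or without a random intercept, has one residual variance for all six observations. It averages the noisier single-day scores with the seven-day means and applies the result at assessment 3. The reported standard error there is then too large. SAP 2 plans no formal hypothesis testing, so the estimates and intervals carry the interpretation. In a small proof-of-concept study, an interval that is too wide could make a real effect on pain or fatigue look inconclusive. These endpoints are also part of the Early Readout Analysis (SAP 5.12.1).

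**Working it through.** **Inputs from the documents.** Three sequences, 1:1:1. Sixty randomized, 48 completers. BPI-SF SDs after baseline adjustment: 1.74 between and 1.5 within participants (Protocol 9.8, SAP 3). Model terms and contrast from SAP 5.8.2.1.

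**Assumptions.** No variance or day-to-day correlation is given for either NRS. The BPI-SF SDs stand in for them, and the split of the within-participant part into a visit-level SD w and a daily SD d is assumed. Days are independent unless stated.

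**1. The plan's own figure.** With 16 per sequence, random-intercept SD 1.74 and residual SD 1.5, generalized least squares for the SAP model gives SE 0.441 for the BPI-SF contrast at assessment 3. Power for 1.0 unit, one-sided 10%, is Φ(1/0.441 − 1.282) = Φ(0.986) = 83.8%. This agrees with the stated figure of more than 80%, so the model set-up is sound.

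**2. Variances at the three NRS assessments.** With between-participant SD b:

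- assessments 1 and 2: b² + w² + d²
- assessment 3 with all seven days: b² + w² + d²/7

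Case A (b 1.74, w 0.5, d 1.4): 3.03 + 0.25 + 1.96 = 5.24, against 3.03 + 0.25 + 0.28 = 3.56.
Case B (b 1.74, w 1.0, d 1.1): 3.03 + 1.00 + 1.21 = 5.24, against 3.03 + 1.00 + 0.17 = 4.20.
Both have a single-day total SD of 2.29, close to the protocol's 2.3.

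**3. Standard error under the standard AR(1) reading.** A random intercept plus equal-variance AR(1) was fitted to each true covariance by minimizing the expected REML criterion (20 per sequence, complete data). The model-based SE was then compared with the true (sandwich) SE of the same estimate.

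| Case | Daily share of within variance | Model SE | True SE | Overstatement |
|---|---|---|---|---|
| A | 1.96/2.21 = 89% | 0.346 | 0.270 | 28% |
| B | 1.21/2.21 = 55% | 0.365 | 0.323 | 13% |
| b 1.2, w 0.5, d 2.0 | 4.00/4.25 = 94% | – | – | 50% |

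With a normal multiplier, the 95% half-width is 1.96 × 0.346 = 0.68 instead of 1.96 × 0.270 = 0.53 in case A, and 0.72 instead of 0.63 in case B.

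**4. Range over the unknown inputs.** With 16 per sequence, the BPI-SF SDs, visit-level correlation of 0, 0.5 or 0.8 and day-to-day correlation of 0 or 0.3:

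| Daily share of within variance | Overstatement |
|---|---|
| 25% | 4% to 5% |
| 50% | 8% to 12% |
| 75% | 16% to 21% |
| 100% | 28% to 36% |

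Alternative SDs (between 1.2, or within 1.0) give 3% to 46%. Applying AR(1) separately within each period brings the low end to about zero (−1%). Correlation between successive days shrinks the effect: at 0.3, 0.5 and 0.7, case A falls from 28% to 23%, 18% and 12%, and case B from 13% to 11%, 9% and 6%. Averages based on only three days shrink it further, since d²/3 replaces d²/7.

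**5. The remedy.** A random intercept with heterogeneous AR(1), the variance differing at assessment 3, was checked in three cases (visit-level correlation 0.5). Model SEs were 0.361, 0.310 and 0.283, against true SEs of 0.369, 0.316 and 0.287, so they agree within about 2%.

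**The case against.** The strongest case against the point is that it is conditional, conservative and of unknown size. Unstructured is the first choice and has no such problem. Heterogeneous AR already fits the SAP's wording. The error widens intervals, so it does not inflate false positives. It touches two secondary endpoints in a Phase 2a study without formal testing. Descriptive summaries of the NRS averages (SAP 5.8, with SDs per SAP 5.1) will show the observed spread. All of this stands and keeps the point minor.

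It does not remove the point. Non-convergence is plausible: a random intercept is redundant beside an unstructured matrix over six visits, which alone has 6 × 7/2 = 21 parameters, with 48 to 60 participants. SAP 5.8.2.1 itself says the model as written has more parameters than needed. How often the fit would fail cannot be derived from the documents, and the risk is lower if the pattern applies only within period. A programmer told to use an autoregressive structure may well choose standard AR(1).

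A reader might infer three stronger claims that the documents do not support:

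- **That the SAP prescribes equal variances.** It leaves the form open.
- **That 13% to 28% is the size of the error.** That range needs NRS variance components the documents do not give, independent days, and a daily noise share of about 55% to 88%.
- **That 22% to 39% of the information is discarded.** Those figures come from squaring the ratio of reported to true SE, but the true SE is the actual precision of the same fallback estimate. The reported interval is what mainly goes wrong. With 16 per sequence and daily shares of 55% and 85%, the true SEs of 0.363 and 0.311 compare with 0.358 and 0.289 under the correct covariance, which is 1% and 8% larger.

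**Conclusion.** The point holds as a gap in specification. Single-day scores and seven-day means share one model, the contrast is read at the averaged assessment, and the fallback does not exclude a single residual variance. If the unstructured fit fails and standard AR(1) is chosen, the SE of the 12-week difference in Pain and Fatigue NRS is overstated. The size is an assumption-based range, from near 0% to about 50%. It rests on BPI-SF SDs or assumed alternatives, an assumed daily noise share, and assumed correlations between days and visits. The primary endpoint and FIQR are not affected. Severity is minor; this is a cheap improvement.

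**What to change.** In SAP 5.8.4, add that for Pain and Fatigue NRS any fallback covariance must allow the residual variance to differ by assessment number, for example heterogeneous AR(1) or a separate variance for assessment 3. Keep Kenward-Roger as planned. The cost is one sentence, one option in the model code, and one or two more variance parameters to estimate. SAP 1 requires an amendment for changes to secondary-endpoint methods before unblinding, so the form should be fixed before the Early Readout Analysis and not chosen after seeing which model converges.

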1.3 Schedule of activities

The Schedules of Activities are provided in [Table 1-1](#) (through Treatment Period 1) and in [Table 1-2](#) (Treatment Period 2 through EOS). Additional study assessments are outlined in Section [1.3.1](#).

Table 1-1: Schedule of Activities (through Period 1)

Procedure	Screen	Run-in	Run-in	12-week Treatment Period: 1											
Visit number	0	1	2	3	4	5	6	7	8	9	10	11	12	13	14
Visit window	up to 28 days	-	±2d	±2d	±2d	±2d	±2d	±2d	±2d	±2d	±2d	±2d	±2d	±2d	±2d
Week	-6	-2	-1	1	2	3	4	5	6	7	8	9	10	11	12
Day	-42	-14	-7	1	8	15	22	29	36	43	50	57	64	71	78
Informed consent	X														
Verification of inclusion/exclusion criteria	X	X													
Demography	X														
Randomization		X													
General medical/ procedure history (including headache history and pain management program) ^a	X														
C-SSRS ^b	X				X										
Serum pregnancy test	X														
Urine pregnancy test		X		X					X			X			
Serology (Hepatitis B, Hepatitis C, and HIV)	X														
IGRA TB test (optional) ^c	X														
Laboratory assessments (full hematology, chemistry, urinalysis)	X	X		X				X				X			
Urine drug screen ^d	X														

Table 1-1: Schedule of Activities (through Period 1)

Procedure	Screen	Run-in	Run-in	12-week Treatment Period: 1											
	0	1	2	3	4	5	6	7	8	9	10	11	12	13	14
Visit number	up to 28 days	-	$\pm 2d$	$\pm 2d$	$\pm 2d$	$\pm 2d$	$\pm 2d$	$\pm 2d$	$\pm 2d$	$\pm 2d$	$\pm 2d$	$\pm 2d$	$\pm 2d$	$\pm 2d$	$\pm 2d$
Visit window															
Week	-6	-2	-1	1	2	3	4	5	6	7	8	9	10	11	12
Day	-42	-14	-7	1	8	15	22	29	36	43	50	57	64	71	78
12-lead ECG ^e	X			X											
Vital signs (blood pressure, pulse, and temperature) ^f	X	X	X	X	X	X	X	X	X	X	X	X	X	X	X
Full physical examination ^g	X														
Brief physical examination ^g		X		X											
Full neurological examination ^h	X														
Pain NRS	X ⁱ	X ⁱ	X ⁱ	X ^j	X ^j	X ^j	X ^j	X ^j	X ^j	X ^j	X ^j	X ^j	X ^j	X ⁱ	X ⁱ
BPI-SF	X			X				X					X		
FIQR	X		X			X				X				X	
Fatigue NRS	X ^j	X ⁱ	X ⁱ	X ^j	X ^j	X ^j	X ^j	X ^j	X ^j	X ^j	X ^j	X ^j	X ⁱ	X ⁱ	X ⁱ
Pressure pain threshold ^k			X												
IMP discontinuation/study withdrawal criteria		X	X	X	X	X	X	X	X	X	X	X	X	X	X
Adverse event review	X	X	X	X	X	X	X	X	X	X	X	X	X	X	X
Concomitant medication review	X ^l	X	X	X	X	X	X	X	X	X	X	X	X	X	X
IMP administration		X(pb)	X(pb)	X	X	X	X	X	X	X	X	X	X	X	X
PK ^m		X		X	X								X		
ADA ^m		X		X	X								X		
IgG (total, subclasses) ^m	X ⁿ	X		X	X			X				X			

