### 5.1.1.2 Study Periods

The maximum study duration per study participant will be 37 weeks.

- Screening Period (Day -42 to Day -15): Eligibility will be assessed during the Screening Period of up to 28 days
- Run-In Period (Day -14 to Day -1): Study participants who have been confirmed eligible to participate in the study will be randomized 1:1:1 to study treatment. During the 2-week Run-In Period, all study participants will receive placebo sc QW and will be blinded to this treatment.

---

- Treatment Period 1 (Day 1 to Day 84): Study participants will receive their randomized treatments for the first 12-week Treatment Period.
- Treatment Period 2 (Day 85 to Day 168): Study participants will receive their randomized treatments for the second 12-week Treatment Period.
- Run-Out Period (Day 169 to Day 182): At the end of both 12-week Treatment Periods, all study participants will receive placebo sc QW during a 2-week Run-Out Period and will be blinded to this treatment.
- Safety Follow-up Period (SFU, Day 183 to Day 218): Study participants who complete both Treatment Periods and Run-Out Period will enter the 5-week SFU Period.
- Study participants who permanently discontinue IMP are encouraged to complete the EOT/EW Visit and the SFU/End of Study (EOS) Visit. In these cases, the SFU will not take place between study Day 183 to Day 218.
- Safety analysis will include periods from Run-In through end of SFU period. Efficacy, PK and PD analysis will include data collected from Treatment Period 1 to end of SFU Period.

Efficacy, PK and PD measurements collected post-Baseline and up to and including Visit 15 will be allocated to Treatment Period 1. Efficacy, PK and PD measurements collected after Visit 15 and up to and including Visit 27 will be allocated to Treatment Period 2.

For the purposes of analysis, data including AEs, IPDs, and medications will be assigned a study period using the rules summarized in Appendix 4 [Section 8.4](#).

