**Table 5-2: Definition of Baseline**

Endpoint	Definition of Baseline
Hematology, serum chemistry, urinalysis, vital signs	Baseline is defined as the most recent value obtained prior to the first dose of IMP in the Run-In Period, or Screening if this is missing.
Efficacy	
Baseline is defined as the measurements on Day 1 (Visit 3, Week 1) prior to administration of treatment or during Run-In Period depending on the endpoint:
 
 
For BPI-SF, the Baseline measurement is at Day 1 (Visit 3, Week 1). If Day 1 measurement is missing, then the Screening measurement will be used.
 
For Pain NRS, and Fatigue NRS, the Baseline measurement will be the average of the 7 days prior to Day 1 (Visit 3, Week 1), not including Day 1 data. If there are <3 assessments available within the 7 days, the Baseline measurement will be missing.
 
For FIQR, the Baseline will be the last assessment before Day 1. This is Day -7 (Visit 2, Week -1) or Screening visit if Day-7 is missing.
 
 
Note that for all endpoints listed above, if a dose of study medication was not received at Visit 3, but the efficacy assessment was performed at Visit 3 (or Visit 2 for FIQR), the Baseline assessment would be defined as above.

Pharmacodynamics (PD)	
Baseline is defined as the latest non-missing assessment performed prior to dosing on Day 1 (Visit 3, Week 1). If Day 1 measurement is missing, the Run-In (Visit 1, Week -2) measurement will be used.
 
Note that if a dose of study medication was not received at Visit 3, but the PD assessment was performed at Visit 3, this would still be used as the Baseline assessment.

Pressure Pain Threshold	
Baseline is defined as the average of the three assessments performed per site, prior to dosing on Day 1 (Visit 3, Week 1).
 
Note that if a dose of study medication was not received at Visit 3, but the Pressure Pain Threshold assessment was performed at Visit 3, this assessment would still be used as the Baseline assessment.

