#### **5.1.4 Handling of Dropouts or Missing Data**

Unless otherwise specified, there will be no imputation of missing data.

For Pain and Fatigue NRS, the 7-day average scores will be calculated based on available data. If there are any missing records in the 7-day periods (inclusive of the assessment visit and the following 6 days), the scores will be calculated as the average amongst the recorded scores, ignoring the missing data. A minimum of 3 completed scores are required to calculate the average; otherwise, the average will be treated as missing. Missing data from visits associated with single assessments will not be imputed.

For details regarding PK data, see [Section 5.5.1](#).

Handling missing or partial missing date and time described in Appendix 2, [Section 8.2](#).

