**Table 5-8: Efficacy endpoint time points**

Endpoint	Baseline measurement	Effect measurement for period 1	Effect measurement for period 2
BPI-SF interference (and other endpoints derived from BPI-SF)	start of Treatment Period 1 Visit 3, D1 pre-dose	pre-dose start of Treatment Period 2 Visit 15, Week 13, D85 (12 weeks of treatment)	Run-Out visit 1 Visit 27, Week 25, D169 (12 weeks of treatment)
Pain and fatigue assessment (NRS)	Run-In visit 2 (starting at D-7 and going to D-1)	Visit 14, Week 12 starting at D78 and going to D84 (12 weeks of treatment)	Visit 26, Week 24 starting at D162 and going to D168 (12 weeks of treatment)
FIQR (and endpoints derived from the FIQR)	Run-In visit 2 Visit 2, D-7	Visit 13, Week 11, D71 (10 weeks of treatment)	Visit 25, Week 23, D155 (10 weeks of treatment)

- BPI-SF interference score is calculated as the mean of the seven pain interference items of the BPI-SF questionnaire. The BPI-SF interference score will be calculated if more than 50% of the total items have been completed on a given administration. For more details on BPI-SF see (Cleeland and Ryan, 1991).

- The FIQR is scored in 3 steps:
  - Step 1. Sum the scores of the items within each of the three domains (domain 1: activities, domain 2: overall impact, and domain 3: symptoms).
  - Step 2. Divide domain 1 score by three, domain 2 score is unchanged, and divide domain 3 score by two. (So if the scores in domains 1, 2 and 3 are 60, 9 and 40, respectively, then domain 1 score divided by three = 20; domain 2 remains unchanged at = 9; domain 3 score divided by two = 20)
  - Step 3. Add the three resulting domain scores to obtain the total Revised Fibromyalgia Impact Questionnaire (FIQR) score. In the example above the total FIQR score would be  $20+9+20 = 49$
  - Missing answers: For unanswered questions the following “weighting” factor should be used. If only  $x$  questions from the first section (function) were answered, one would weigh the summated score of the  $x$  questions by  $9/x$  (as there are 9 items in the function set of questions) Likewise the second section (overall impact) would have a weighting of  $2/x$  (there are only 2 items) and the third section (symptoms) would have a weighting of  $10/x$  (there are 10 items).

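### The Period 1 Pain and Fatigue NRS average has no stop at the Visit 15 dose, and it conflicts with the SAP's period-allocation rule when Visits 14 and 15 are fewer than 6 days apart

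*SAP*

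**What the plan says.** - **Endpoint rule.** SAP 5.8.4 uses "the average of Visit 14 and the following 6 days for Treatment Period 1", with the same construction at Visit 26 for Period 2, and requires at least 3 valid entries. SAP 5.1.4 describes the 7-day period as "inclusive of the assessment visit and the following 6 days". Neither section mentions the next period's first dose.
- **Nominal days.** SAP Table 5-8 shows the Period 1 window as D78 to D84, with Visit 15 on D85.
- **Period allocation.** SAP 5.1.1.2 keeps post-baseline efficacy data up to and including Visit 15 in Period 1, and then: "Efficacy, PK and PD measurements collected after Visit 15 and up to and including Visit 27 will be allocated to Treatment Period 2". It does not say whether this applies to each diary entry or to the derived Visit 14 average. Sections 5.8.4 and 5.1.4 do not refer to it.
- **Visit windows.** Protocol Tables 1-1 and 1-2 allow ±2 days at both Visit 14 and Visit 15.
- **Other boundaries.** For baseline NRS, SAP Table 5-2 says "the Baseline measurement will be the average of the 7 days prior to Day 1 (Visit 3, Week 1), not including Day 1 data". The BPI-SF value at Visit 15 is specified as pre-dose (SAP 5.8.2 and Table 5-8).

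**The concern.** The baseline NRS average and the Visit 15 BPI-SF value are both tied to the dose. The Period 1 NRS average is tied only to Visit 14. If Visit 14 is late, Visit 15 early, or both, seven calendar days from Visit 14 run past the Visit 15 dose. One SAP rule then places the later entries in the Period 1 endpoint and another places them in Period 2. Two programmers could derive different scores from the same diary.

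This matters for Sequence 2, the only group that changes treatment at Visit 15. It supplies 20 of the 40 planned Period 1 placebo participants, and the design relies on it for the within-participant comparison of placebo with rozanolixizumab. Protocol 2.3 lists headache, pyrexia, arthralgia and myalgia among the adverse reactions. Soon after a first infusion these could raise pain or fatigue ratings and so make the placebo score look worse. An early benefit would act in the other direction. The sign of any bias is therefore not known.

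**Working it through.** **Inputs**
- Visit 14: D78 ± 2, so D76 to D80 (Protocol Table 1-1).
- Visit 15, first Period 2 dose: D85 ± 2, so D83 to D87 (Protocol Table 1-2).
- Average: the Visit 14 day plus the next 6 days (SAP 5.8.4, 5.1.4).

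**1. The plan's own window.** 78 + 6 = 84, which is before 85. At nominal timing no entry reaches the dose day, and Table 5-8 is reproduced.

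**2. Effect of the visit windows.** Let g be the Visit 15 day minus the Visit 14 day. The smallest g is 83 − 80 = 3 and the largest is 87 − 76 = 11. The last averaged day is Visit 14 + 6, so:
- entries dated after the Visit 15 day = max(0, 6 − g)
- entries dated on or after the Visit 15 day = max(0, 7 − g)

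| Gap g (days) | In-window pairs (of 25) | Entries after the Visit 15 day | Entries on or after it | Entries before it |
|---|---|---|---|---|
| 3 | 1 | 3 | 4 | 3 |
| 4 | 2 | 2 | 3 | 4 |
| 5 | 3 | 1 | 2 | 5 |
| 6 | 4 | 0 | 1 | 6 |
| 7 to 11 | 15 | 0 | 0 | 7 |

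The 5.8.4 and 5.1.1.2 rules disagree when g is 5 or less. At g = 3, the three later entries alone would meet the 3-entry minimum if the other four were missing.

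**3. Frequency.** The documents give no distribution of visit days. Assuming uniform and independent days within the windows:
- at least one entry after the Visit 15 day: (1 + 2 + 3)/25 = 6/25 = 24%
- mean number of such entries per participant: (1×3 + 2×2 + 3×1)/25 = 10/25 = 0.4
- counting the dose day as well: (1 + 2 + 3 + 4)/25 = 10/25 = 40% of participants, and (1×4 + 2×3 + 3×2 + 4×1)/25 = 20/25 = 0.8 entries per participant

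**4. Shift in the mean.** Suppose each entry after the dose day is raised by r points. The documents do not give r, so 1 to 3 is an assumption. The Sequence 2 Period 1 mean moves by 0.4 × r/7:
- r = 1: 0.06
- r = 2: 0.11
- r = 3: 0.17

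Sequence 2 is half of the planned Period 1 placebo group, so that group's simple mean moves by half as much: 0.03, 0.06 and 0.09. The scale runs from 0 to 10. Counting the dose day at r = 2 gives 0.8 × 2/7 = 0.23 for Sequence 2 and 0.11 for pooled placebo.

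**5. Other readings of the text**
- Fixed days D78 to D84, whatever the actual Visit 14 date: one entry (D84) falls after the dose day if Visit 15 is on D83, and none if it is on D84.
- A ±2-day window counted from the previous visit: g runs from 5 to 9, so at most one entry falls after the dose day.
- SAP 5.1.1.2 applied to each diary entry: no entry after the Visit 15 day remains, and only that day's own entry is in question.

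**The case against.** The best defence is that the SAP already has a boundary. Applied entry by entry, 5.1.1.2 removes every day after Visit 15 from the Period 1 score. Section 5.8.4 refers to Table 5-8 for time points and describes the NRS data as coming from the twelfth week, and SAP Table 5-1 ends Period 1 at Day 84. The intention to stay within Period 1 is clear. What these passages do not do is say which rule governs when actual visit dates move. SAP 5.8 summarises the average of the measurements related to a given visit, which points toward allocation by visit rather than by diary day.

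A reader might infer that 40% of participants and up to 4 of 7 entries are affected. Those figures count the Visit 15 day as exposed. Assessments in the weekly columns are to be done before dosing unless otherwise specified, and both NRS items look back 24 hours (Protocol 8.1.2 and 8.1.5), so that day's entry normally describes placebo. One gap remains: under SAP 5.8 the latest of several same-day entries is used, and that one could be post-dose.

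The objection that the impact is small largely stands. Protocol 4.3 places PD steady state after 6 weeks, so a benefit within 1 to 3 days is unlikely to matter, and Protocol 2.3 describes headaches as mostly mild to moderate. Early adverse reactions remain possible. SAP Section 2 plans no formal hypothesis testing.

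The same wording lets the Visit 26 average run past Visit 27 into Run-Out placebo. It would be wrong to treat this as comparable. Protocol 4.2 says IgG takes too long to return towards Baseline for a washout to be feasible, so a few days of Run-Out are hardly a change of treatment, and Sequence 3 stays on placebo.

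**Conclusion.** The SAP gives two rules that disagree about the same diary entries whenever Visits 14 and 15 are fewer than 6 days apart, which the protocol permits. Under the literal 5.8.4 rule, up to 3 of 7 entries in a Sequence 2 placebo score can postdate its first rozanolixizumab dose. The maximum follows from the visit windows, taken as ±2 days around the nominal days. The 24% and the 0.4 entries per participant depend on the assumed uniform, independent visit days, and the point shifts depend further on the assumed rise per entry.

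The documents do not support saying that the plan will mix treatments: whether it does depends on which rule the programmer applies. The likely effect on group means is small, it concerns two secondary endpoints, and the primary BPI-SF endpoint is untouched. The conflict is still worth removing because the endpoint is not uniquely defined and the correction is cheap.

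**What to change.** In SAP 5.1.4, 5.8.4 and Table 5-8, define the NRS endpoint as the mean of diary entries from Visit 14 onward that precede the actual first dose of the next period, over at most 7 days, keeping the 3-entry minimum. State how the Visit 15 day is handled:
- **Counted if recorded pre-dose.** This agrees with 5.1.1.2, which keeps data up to and including Visit 15. It needs an entry time to compare with the dose time, and a rule that a later same-day entry does not replace the pre-dose one.
- **Excluded.** This mirrors the baseline rule, but 5.1.1.2 then needs a stated exception for NRS.

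Apply the same wording at Visits 26 and 27 for consistency.

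The cost is a few lines of text and one programming condition. SAP Section 1 requires an amendment if secondary-endpoint methodology changes before unblinding. Some means will rest on 3 to 6 entries instead of 7. If the Visit 15 day is excluded, a 3-day gap leaves exactly 3 entries, so one missed entry makes the endpoint missing. Counting a pre-dose entry on that day leaves 4.
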